6.2.10. Duration of fever

Duration of fever [days] = (Date of stop of fever – Date of start of fever +1)

6.2.11. Duration of Klg10 exposure

Duration of Klg10 exposure is defined as the number of weeks from Day 1 to the date of Last Dose of Klg10

6.2.12. Duration of Klg10 infusion

Duration of Klg10 infusion is defined, for each infusion, as

Duration of Klg10 infusion [minutes] = Date/time of stop of Klg10 infusion – Date/time of start of Klg10 infusion

6.2.13. Duration of infusional AE

Infusional AEs are AEs that begin during or within 72 hours after an infusion.

Duration of AE [hours] = Date/time of stop of AE – Date/time of start of AE

6.2.14. Duration of noninfusional AE

Duration of AE [days] = Date of stop of AE – Date of start of AE + 1

6.2.15. Fever

Fever is defined as a body temperature  $\geq 38^{\circ}\text{C}$  ( $\geq 100.4^{\circ}\text{F}$ ).

6.2.16. Pediatric

A patient will be considered as a pediatric, if he/she is between  $\geq 2$  to  $\leq 17$  years old at the time of the screening. Here, age is defined as calendar year age (e.g., 11.99 years = 11 years old).

This document is confidential.

6.2.17. Prior/Concomitant medication

A medication is regarded as “prior” if the stop date of the event is prior to the date of first infusion, irrespective of the start date.

The medication is regarded as “concomitant” if the start date or stop date is between the date of first infusion (included) and the day of study termination (included).

The medication is regarded as “concomitant” if ticked as ongoing on the CRF.

6.2.18. Start Day of previous/concomitant medication

If medication starts before date of first infusion:

Start Day of Medication = Date of start of medication – Date of first infusion

If medication starts at/after date of first infusion:

Start Day of Medication = Date of start of medication – Date of first infusion + 1

Incomplete start dates of medication will not be imputed. Start day of medication will be missing.

6.2.19. Study Day

Study Day is defined relative to Day 1. Thus, the study day of an event is calculated as:

Study Day = Event date – Date of Day 1 + 1.

6.2.20. Study Duration/Length

Study Duration (in days) is computed as (Date of termination – Date of first infusion + 1)

This is equivalent to the definition of Day of Study Termination.

6.2.21. Study Visit

Study Visit is the nominal visit as recorded on the CRF.

6.2.22. Time since PID Diagnosis

Time since diagnosis [months] = ((Date of Screening – Date of diagnosis)+1)/30

6.2.23. Time to Onset of infusional AE

Time to Onset of AE [hours] = Date/time of start of AE – Date/time of start of infusion at respective infusion (1st infusion, 2 infusion, etc.)

6.2.24. Time to Onset of noninfusional AE

Time to onset of AE [days] = Date of start of AE – Date of first infusion

### 6.3. Missing Data

Every effort will be made to obtain required data at each scheduled evaluation from all patients. All available data will be included in the analyses and will be summarized as far as possible. Unless otherwise specified, there will be no substitution of missing data, i.e., missing data will not be replaced; missing data will be

This document is confidential.

handled as 'missing' in the statistical evaluation. Imputation methods used to analyze the primary efficacy endpoint and other efficacy endpoints will be detailed in the relevant sections where it applies.

#### 6.3.1. Efficacy endpoints

Patients who discontinued before completing the study will lead to missing data on the primary efficacy endpoint. Multiple Imputation (MI) will be used to impute the missing data in primary efficacy endpoint. The details of the imputation process and sensitivity analyses to assess the robustness the primary efficacy results are described in Section 8.1.4.5. Methods for dealing with missing or incomplete data where any imputation of the data is planned for other efficacy endpoints are covered in the relevant sections.

#### 6.3.2. Safety endpoints

Partial or missing dates of safety data will be imputed according to the most conservative approach.

##### 6.3.2.1. AEs

For missing or incomplete start dates, if the month/year is the same as the Day 1 month/year then the date will be set to the date of Day 1. In other cases, missing days will be imputed as the day component of Day 1; missing months/years will be imputed as the month/year of Day 1. Incomplete end dates are assumed to have ended on the study completion date. Actual values will be presented in data listings.

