6.2.8. Duration of infection

Duration of infection [days] = Date of stop of infection – Date of start of infection + 1

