## 10.3. Adverse Events / Adverse Drug Reactions

Adverse events (AEs) will be coded using MedDRA to give a PT and a SOC term for each event. At the end of the study, AEs will be recoded applying the latest available MedDRA version available at this time point.

Adverse events temporally associated with the infusion are AEs occurring during infusion or within 72 hours after the end of infusion and are defined as infusional AEs.

Summary tables will be based on treatment-emergent adverse events (TEAEs), defined as those events with onset date/time at or after the first Klg10 infusion until the patient's last study visit.

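### The imputation rule for partial AE start dates has no upper bound, so it can place onset after the AE's own stop date or after the last study visit

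*SAP*

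**What the plan says.** SAP 6.3.2 sets the principle for safety data: "Partial or missing dates of safety data will be imputed according to the most conservative approach". SAP 6.3.2.1 then gives the rule for AEs. For a missing or incomplete start date, "if the month/year is the same as the Day 1 month/year then the date will be set to the date of Day 1". In every other case, "missing days will be imputed as the day component of Day 1; missing months/years will be imputed as the month/year of Day 1". For end dates, "Incomplete end dates are assumed to have ended on the study completion date". Listings show the actual values, so the imputed dates serve the tables and derived variables.

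Two other sections use the start date. SAP 6.2.14 defines "Duration of AE [days] = Date of stop of AE – Date of start of AE + 1". SAP 10.3 bases the AE summary tables on treatment-emergent AEs, which it defines by "onset date/time at or after the first Klg10 infusion until the patient's last study visit".

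The study completion date appears in 6.3.2.1 only for incomplete end dates. No section limits an imputed start by a recorded stop date or by the last visit.

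**The concern.** The rule builds onset from Day 1 alone and ignores two facts that are usually known: when the AE stopped and when the patient left the study. Two wrong results can follow.

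- **Onset after the AE ended.** The imputed date contradicts a recorded date, and the 6.2.14 duration becomes zero or negative.
- **Onset after the last visit.** An AE that occurred on treatment falls outside the TEAE window and leaves the TEAE rows of SAP 10.3.1 and the SOC/PT tables of 10.3.2. That loses a safety event, which is the opposite of the principle in 6.3.2.

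**Working it through.** The plan gives no figure to reproduce, so the check applies the rule as written.

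**Inputs.** The start-date and end-date rules are from SAP 6.3.2.1, the duration formula from 6.2.14 and the TEAE window from 10.3. The visit schedule is from SAP 3.4. Nominal termination is Day 1 + 12 × 28 + 28 = Day 1 + 364 days (28-day schedule), or Day 1 + 16 × 21 + 21 = Day 1 + 357 days (21-day schedule). By the study-day definition in 6.2.19 these are study days 365 and 358.

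**Step 1: onset against a known stop date.** Take Day 1 = 25-Feb-2019 and an AE with start UN-Aug-2019 and stop 12-Aug-2019. The missing day becomes 25, so onset is 25-Aug-2019. Duration = 12 − 25 + 1 = −12 days.

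**Step 2: onset against the last visit, day missing.** Take Day 1 = 25-Mar-2020. Nominal termination is 24-Mar-2021 (28-day) or 17-Mar-2021 (21-day). A start of UN-Mar-2021 becomes 25-Mar-2021, which is 1 or 8 days after the last visit. If the end date is also incomplete it is set to study completion, and the duration is 0 or −7 days.

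**Step 3: onset against the last visit, only the year known.** Take Day 1 = 10-Oct-2019 and an onset known only as 2020. The rule gives 10-Oct-2020, study day 367. Nominal termination is 8-Oct-2020 (28-day) or 1-Oct-2020 (21-day). In general, an AE known only to the second calendar year lands on the anniversary of Day 1: study day 366, or 367 when the span contains 29 February. Both lie beyond days 365 and 358.

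**Step 4: how often onset falls after the stop date.** These shares apply only to AEs with a missing start day and a known stop date. The enumeration covers 365 Day 1 dates and every on-study onset day. It truncates the stop date at termination and sets a non-existent date to month end. The simulation draws 50,000 AEs per length, with Day 1 uniform over 2019, onset uniform over the next 364 days and the stop date not truncated.

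| AE length (days) | Enumeration, 28-day | Enumeration, 21-day | Simulation |
|---|---|---|---|
| 1 | 48% | 47% | 47% |
| 3 | 42% | 42% | 41% |
| 7 | 32% | 31% | 30% |
| 14 | 18% | 17% | 15% |

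The three sets agree within about three percentage points. About 1% of imputed dates do not exist (for example 31 June).

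**Step 5: how often onset falls after the last visit.** In the same enumeration, 3.8% (28-day) and 2.2% (21-day) of all day-missing AEs are imputed after nominal termination. These are the AEs with onset in the termination month. For such an AE, the shares of Day 1 dates that give a post-visit onset are:

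| Schedule | Early visit | Nominal visit | Late visit |
|---|---|---|---|
| 28-day (±4 days) | 81% | 94% | 7% |
| 21-day (±3 days) | 61% | 71% | 81% |

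For patients who terminate early, the corresponding share is about 47% to 48%.

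**The case against.** The strongest reply has five parts.

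1. **Partial dates may be rare.** Under Protocol 4.4.2 the diary is to be completed daily and is reviewed at each visit, and events up to one hour after infusion are recorded on site. A 1-day AE with a known stop date but an unknown start day is an unlikely record. This stands as a limit on size: the documents give no rate. Partial dates remain foreseeable, because the same section has blank or illegible diary fields entered as missing, and Protocol 6.11 allows early termination by telephone.
2. **Infection duration is not shown to be affected.** A reader might infer that secondary endpoint 9 inherits negative durations, since 6.2.8 computes "Duration of infection [days] = Date of stop of infection" minus the start date plus 1. The documents do not support this. SAP 6.3.2.1 is a safety rule. SAP 6.3 leaves missing data unreplaced by default, 6.3.1 defers efficacy imputation to the relevant sections, and 8.2.7 gives no date rule. On the text, a partly dated infection has a missing duration for that endpoint.
3. **No AE-duration table is listed.** The outputs in 10.3.1 to 10.3.3 are counts and percentages. This stands, so negative AE durations matter only wherever 6.2.14 is used.
4. **The last visit can move.** The windows apply after each infusion, so the visit can fall after the anniversary of Day 1. In Step 3, a net delay of two days on the 28-day schedule brings the AE back into the TEAE window. The post-visit figures are therefore nominal-schedule figures.
5. **The AE does not vanish.** It stays in the any-AE row of 10.3.1 and in the listings.

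None of this supplies the missing bound.

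**Conclusion.** The defect holds and should be corrected before database lock. Read literally, 6.3.2.1 can give an onset after the AE's own stop date, an onset after the last visit, or a date that does not exist. The second result removes an AE from the TEAE rows and SOC/PT tables, contrary to the principle in 6.3.2.

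The sizes are roughly 47%, 30% and 15% for 1-, 7- and 14-day AEs (onset after stop), and about 3.8% and 2.2% on the 28- and 21-day schedules (onset after last visit). They rest on uniform onset, illustrative AE lengths and nominal visits. They are shares of records with a missing start day, not of all AEs.

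A reader might also infer that the primary infection count loses events. That is not shown: SAP 8.1.2 searches AE preferred terms and states no TEAE restriction.

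**What to change.** Amend SAP 6.3.2.1 as follows, using every known date part.

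1. If the known parts of the start date, or the stop date, show that the AE began or ended before Day 1, keep it as pre-treatment.
2. Otherwise impute the later of Day 1 and the first day of the known month, or 1 January of the known year if the month is missing.
3. Cap the result at the earlier of the recorded stop date and the last study visit.
4. Count the AE as treatment-emergent unless its known date parts show otherwise.

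For an on-study AE this rules out negative durations and post-visit onsets by construction. It also avoids non-existent dates, because the first of a month always exists. Step 1 is needed because a month or stop date before Day 1 leaves no admissible on-study date.

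The cost is one paragraph and a few lines of code. Some partially dated AEs move to earlier onsets.

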## 6.7 TREATMENT VISITS

Patients will be required to return to the study site for each visit every 21 ( $\pm$  3) days or every 28 ( $\pm$  4) days depending on treatment regimen for a period of 48 weeks – see

Table 1.1, Time and Events Table for 28-day Infusion Schedule and Table 1.2, Time and Events Table for 21-day Infusion Schedule.

Each patient will be treated with Klg10 as reported in the Section 6.5, Treatment Regimen, and undergo the following tests and procedures:

- A physical examination (evaluation of all body systems) with an evaluation of vital signs (blood pressure, heart rate, and temperature); body weight will be collected at each visit for pediatric patients and at weeks 12, 24, 36, and 48 for adults.
- Collection of blood (pre-infusion) to measure IgG levels
- Collection of blood (pre-infusion) to measure IgG subclasses (IgG1, IgG2, IgG3 and IgG4) and specific antibodies (anti-Haemophilus influenza type b, anti-Tetanus toxoid, anti-pneumococcal polysaccharide and anti-measles) at infusions 5, 9, and 13 for the 28-day infusion schedule and at infusions 7, 11, and 17 for the 21-day infusion schedule.
- Collection of blood samples (pre-infusion) for hematology and chemistry.
- Collection of urine samples (pre-infusion) for urinalysis.
- Collection of blood and urine samples for intravascular hemolysis testing (post-infusion).(at infusion 5 for the 28-day infusion schedule or at infusion 7 for the 21-day infusion schedule).
- Recording of all AEs and SAEs, including any infections, fever episodes, and hospitalization.
- Recording of all concomitant medication, including use of antibiotics for any kind of infection.
- Review of Patient Diary (with data collection) and dispensing.
- Record Klg10 administration information (batch number, dosage, amount of product infused, infusion start and end time, infusion rate).
- Record days off work/school/other major activities due to infections.
- At infusion 5 (28-day infusion schedule) or at infusion 7 (21-week infusion schedule), only for those patients that consent to the PK portion of the study (PK Evaluation Set), additional blood samples will be collected for evaluating total IgG levels, IgG subclasses, and specific antibodies, at the time points as described at Section 8.4 Pharmacokinetic (PK) Assessment (PK Evaluation Set):

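### SAP 6.3.2.1 moves every incomplete AE end date to the study completion date even when the month and year are known, so an analysed duration of days can become many months

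*SAP*

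**What the plan says.** SAP 6.3.2 states the principle for safety dates: "Partial or missing dates of safety data will be imputed according to the most conservative approach". SAP 6.3.2.1 then applies it to AEs.

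- **Start dates.** Known parts are kept and only the missing parts are filled in: "missing days will be imputed as the day component of Day 1", with a matching rule for missing months and years.
- **Stop dates.** There is a single sentence: "Incomplete end dates are assumed to have ended on the study completion date". It has no branch for a known month or year.
- **Listings.** "Actual values will be presented in data listings".

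Durations are then differences of dates. SAP 6.2.8 gives "Duration of infection [days] = Date of stop of infection – Date of start of infection + 1", and SAP 6.2.10 gives "Duration of fever [days] = (Date of stop of fever – Date of start of fever +1" for fever. SAP 6.2.13 gives "Duration of AE [hours] = Date/time of stop of AE – Date/time of start of AE" for infusional AEs, and 6.2.14 uses whole days for the other AEs.

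For data outside the safety rules, SAP 6.3 makes no substitution unless another section specifies one. SAP 6.3.1 refers efficacy endpoints other than the primary to their own sections. Sections 8.2.7 (other infections) and 8.2.8 (fever) contain no rule for incomplete stop dates.

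**The concern.** A partial stop date still carries information. If the site knows that an event ended in March, every possible stop date lies in March. The stop-date rule discards this and places the end at study completion, while the start-date rule in the same section keeps what is known. An appeal to conservatism does not justify the difference: the worst value compatible with a stop some time in March is 31 March.

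What is at stake is the mean and maximum of any duration summary that uses the imputed dates. One such record can set the maximum, and a small share can move the mean. The wording also leaves room for two programmers to report different results for endpoints 9 and 11, because the SAP does not say whether those durations use AE dates imputed under this rule.

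Two smaller gaps sit in the same sentence. The study completion date is not defined as the patient's or the trial's, and SAP 6.2.5 defines completion only for patients who received all doses and attended the termination visit. Stop dates that are wholly missing, or events still ongoing, are not literally covered.

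**Working it through.** The plan gives no figure on this point, so there is nothing to reproduce. The check is date arithmetic with the SAP's own formulas.

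**Inputs from the documents.** Duration = stop − start + 1 (SAP 6.2.8, 6.2.10). With on-schedule visits, termination at week 52 falls on Day 1 + 52 × 7 = 365 (28-day schedule), and at week 51 on Day 1 + 51 × 7 = 358 (21-day schedule).

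**Assumed inputs.** Calendar dates, true event lengths, evenly spread onset, and the share q of stop dates lacking only the day. The documents give none of these. The study completion date is taken as the patient's own termination date.

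**1. One record.** Day 1 is 15 January 2020, termination is 13 January 2021 (Day 365), the AE starts on 10 March 2020, and the stop is an unknown day in March 2020.
- SAP rule: 10 March 2020 to 13 January 2021 is 309 days, plus 1 = **310 days**.
- Latest date the record allows: 31 − 10 + 1 = **22 days**.

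**2. Average over onset days.** A 3-day AE with only the stop day missing, onset on any day that lets it finish before termination:
- SAP rule: durations run from 365 down to 3 days, mean (365 + 3)/2 = **184** (28-day schedule); from 358 down to 3, mean **180.5** (21-day schedule). About 84% of onset days give more than 60 days.
- Last day of the known month, capped at termination: at most 3 + 30 = **33** days, and about **17 to 18** on average (Day 1 set to 1, 15 or 31 January).

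**3. Reaction on an infusion day with a partial stop date.** The SAP rule gives 365 days (infusion 1) down to 29 (infusion 13), mean 197, on the 28-day schedule. On the 21-day schedule it gives 358 down to 22, mean 190.

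**4. Effect on a mean duration.** Assume true durations of 10 days and onset s uniform over 0 to 364. The mean imputed duration is 364 − 182 + 1 = 183 days, and the mixture mean is (1 − q) × 10 + q × 183. Keeping the known month adds at most 30 days to the true stop, so an affected record is at most 40 days and the mean is at most (1 − q) × 10 + q × 40.

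| q | SAP rule | Change | Known month kept (upper bound) |
|---|---|---|---|
| 1% | 9.90 + 1.83 = 11.7 | +17% | 10.3 |
| 2% | 9.80 + 3.66 = 13.5 | +35% | 10.6 |
| 5% | 9.50 + 9.15 = 18.7 | +87% | 11.5 |

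With true durations of 7 days and q of 1%, 5% or 10%, the SAP rule gives 6.93 + 1.83 = 8.8, 6.65 + 9.15 = 15.8 and 6.30 + 18.30 = 24.6 days. In none of these cases does the median move, because the affected records are a small minority at the upper end.

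**5. Which outputs use a stop date.**
- Primary infection rate (SAP 8.1.2): event counts over observation time. Not affected.
- Proportion of infusions with a temporally associated AE against 0.4 (SAP 10.1.2): depends on onset. Not affected.
- AE durations (SAP 6.2.13, 6.2.14): affected as defined, but the AE tables in SAP 10.3 are counts and percentages and none is a duration table.
- Endpoints 9 and 11 (SAP 8.2.7, 8.2.8): affected only if their dates come from imputed AE records.

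**The case against.** The best defence is about reach. The rule stands under safety endpoints, and 6.3.2 confines it to safety dates. Infection and fever durations are efficacy endpoints. SAP 6.3.1 refers their imputation to 8.2.7 and 8.2.8, which plan none, so the default of no substitution in 6.3 applies. Protocol 8.1.5 and 8.1.6 send infection and fever information, including the days to resolution, to dedicated eCRF pages, and only the primary endpoint dataset is stated to be derived from AE data (SAP 8.1.2). On this reading, no table that the SAP names is distorted.

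The defence can add that partial stop dates should be uncommon, since diaries are filled in daily, reviewed at visits every three or four weeks, and subject to queries. The error also lengthens durations, so it cannot flatter the product. The endpoints are descriptive with no success criterion on duration, and medians are reported beside means.

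Most of this stands, and it keeps the severity low. It does not make the rule right, and it does not close the question for endpoints 9 and 11. Protocol 6.7 lists "Recording of all AEs and SAEs, including any infections, fever episodes, and hospitalization" as one item, and Protocol 4.4.2 sends a confirmed diary fever to the AE eCRF page, so AE records are a plausible source. Protocol 4.4.2 also has blank or illegible diary fields entered as missing and bars diary corrections after site review, so some partial dates are foreseeable.

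**Conclusion.** The point holds as a low-severity defect. Wherever the rule is applied, it can produce durations that the recorded data exclude, such as 310 days against a possible 22, and conservatism does not call for that.

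A reader might infer more than this:

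- **That the reported infection and fever durations will be wrong by a large factor.** The documents do not support this. The SAP does not say that the rule feeds endpoints 9 and 11, and its general default points the other way. Even if it does, the illustrated rise for 10-day infections is 17% to 87%, and it rests on assumed shares of 1% to 5%. A larger effect needs shorter events or more partial dates, and the documents give no figure for either.
- **That the efficacy or safety conclusion is at risk.** It is not: neither the primary rate nor the 0.4 criterion uses a stop date.
- **That the database will hold false durations.** The listings show the actual values; only analysed durations change.

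The size is therefore conditional. It depends on the share of partial stop dates, on the true durations, on onset being spread over the year, and on reading the study completion date as the patient's own. Means and maxima are exposed; medians barely are.

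**What to change.** Replace the stop-date sentence in SAP 6.3.2.1 with a rule that keeps the known parts:

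- Month and year known: last day of that month. Only the year known: 31 December. In both cases, cap at the patient's date of termination.
- Stop date wholly missing, or event ongoing: the patient's date of termination.
- Use the date of termination, as SAP 6.2.7 already does, in place of the undefined study completion date.

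Add one sentence to 8.2.7 and 8.2.8 stating that endpoints 9 and 11 either use complete dates only or follow this same rule.

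The cost is a few SAP sentences and minor programming. No data collection changes.
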